**Specific Aim 3 (exploratory): To measure metabolite changes induced by T in infants with XXY.**

**Hypothesis:** Circulating metabolites involved in energy metabolism, specifically long chain acyl-carnitines (LCAC) and branched-chain amino acids (BCAA), will be lower due to improved mitochondrial function in T treated boys; T will favorably alter pathways involved in energy metabolism. **Approach:** LCAC and BCAA will be quantified at baseline and 12 weeks in the first 20 subjects. An unbiased platform of over 4,000 metabolites will also be performed to identify pathways that are differentially regulated with T treatment.

[figure not shown]
Assessing short-term safety and efficacy of T treatment in infants with XXY will provide the first evidence for establishing standard of care practices, with a planned extension for long-term outcomes. These results will generate preliminary data on mechanisms of the effects of T during the critical mini-puberty period for the development of future work, such as sex steroid-induced epigenetic modifications. Mentors with expertise in neurodevelopment, cardiometabolic outcomes, metabolomics, and clinical trials will optimize career development and foster expertise in gonadal and cardiometabolic function in children with sex chromosome aneuploidies.

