**Consent.** When a child is identified through clinic or other method identified above, a member of the study team will contact the parent to inform them of the opportunity to participate in a study. In many cases, the parents will contact the PI, PRA or genetic counselor of the eXtraordinary Kids Clinic after hearing about the study from one of the above sources. Prior to any information being collected, verbal consent to ask questions pertaining to the inclusion/exclusion criteria will be obtained. A member of the study team will describe the study and will offer to email/mail the consent form to the parents so the parents have ample time to review prior to deciding whether to schedule the first visit and enroll in the study.

Prior to any research procedures being performed, a study team member will review the consent form in person in a private location. Both verbal and written consent will be required from a parent or legal guardian to enroll in the study. All of the subjects in this protocol are infants and therefore too young to assent/consent to research participation themselves. To minimize coercion, parents will not be paid for enrolling their child in the study and only reimbursement for reasonable travel will be provided. We will emphasize to parents their child's participation is entirely voluntary and can be withdrawn at any time. As part of the consent process, parents will be asked to summarize the study in their own words to ensure comprehension, and parents will have the opportunity to ask questions. If the consenting parent does not speak English, an interpreter will assist with the consent process and a short-form consent document in the parent's preferred language will be completed. If the consenting parent is blind, illiterate, or with reading limitations, the entire consent form will be read to the subject and witnessed by someone outside of the study team.

**Randomization.** Subjects will be randomized 1:1 using block randomization in groups of 20 to 1) receive T treatment in the first 12 weeks followed by placebo, or 2) placebo for the first 12 weeks followed by T. Investigational Drug Services at CHCO will generate the automated randomization list and dispense the study drug to maintain allocation concealment. All investigators and parents will remain blind to the intervention group.

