**F. Data Analysis Plan:**

The primary outcome for **specific aim 1** is the change in %BF z-scores between baseline and 12 weeks between treatment groups. Z-scores will be calculated using published norms for age, and the difference between groups will be assessed with a two-sided t-test using an alpha of 0.05. Allowing for a 10% drop-out rate, a sample size of 27 in each group gives us 80% power to detect a difference down to 0.5 z-score change between groups, and >99% power to detect the change score we observed in our pilot study (1.0 z-score change) assuming a variance of 0.65 per our pilot data. We will next use regression models with treatment group, baseline %BF, age of enrollment and feeding method as explanatory variables to assess absolute %BF at 12 weeks. Secondary analyses will include change in %BF z-scores from 12 to 24 weeks 1) in the group receiving T first (are the effects of T maintained or lost?) and 2) in the group receiving T second (does later T have the same effect?). We will analyze anthropometric measurements and serum biomarkers similarly.

For **specific aim 2**, the change in standard scores on developmental assessments will be analyzed in a similar fashion as in specific aim 1. Based on our pilot data, our sample size will yield 80% power to detect a difference between groups of 23 percentile points on the AIMS composite. Secondary analysis will include the changes in scaled scores for the individual Peabody domains and AIMS subtests, the Bayley composite scores, and the ABAS composite at 12 and 24 weeks. Gonadal function and safety outcomes will be compared between subjects on T and placebo using descriptive statistics.

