For **specific aim 3 (exploratory)**, we will compare C14:1 concentrations (an easily identified LCAC) between treatment groups at 12 weeks using two-sided t-tests, hypothesizing C14:1 will be lower in the T treated group (representing improvement in fatty acid oxidation and energy metabolism). This aim is exploratory; with 10 subjects per group we will have 80% power to detect a difference of 1.3 SD with a two-sided alpha of 0.05. Then, paired t-tests will be used to compare C14:1 before and after T treatment (5 paired samples), with similar power. We will analyze secondary outcomes including other LCAC and BCAA (leucine, isoleucine, and valine) in a similar fashion. Next, we will use principle component analysis on the entire dataset from the comprehensive untargeted analysis to identify patterns and pathways altered with T treatment. The spectra data file from the non-targeted metabolomics panel will be uploaded to MetaboAnalyst, and the software will be used for Metabolite Set Enrichment Analysis as well as Pathway Enrichment Analysis. We will have >80% power to detect at least 2-fold changes between T treated and untreated using a significance level of 0.0001 (less than two false positives based on the conservative Bonferroni correction for multiple comparisons). We will also input the analytes into known KEGG pathways of energy metabolism to look for pathway enrichment.

Table 2. Summary of primary and secondary outcome measures for each Specific Aim (SA).

SA	Primary Outcome	Weeks		Measurement Tool
		12	24	
SA 1: Cardiometabolic	Change %BF z-scores from baseline	X		PeaPod
	Secondary Outcomes			
	Change %BF z-scores from baseline		X	PeaPod
	Change in height, weight, weight-for-length and waist circumference z-scores from baseline	X	X	Physical exam measurements
	Serum leptin, lipids, and insulin	X	X	Immunoassays in CCTSI core laboratory
SA 2	Primary Outcome			

	Change in motor composite from baseline	X		AIMS percentile composite score (all domains)
	Secondary Outcomes			
	Serum LH, FSH, INHB, AMH, E2 and Total T	X	X	Immunoassay and LC/MS ([name] lab)
	Change in gross and fine motor scaled scores	X	X	Scaled scores on all PDMS-2 domains, AIMS
	Cognitive and Language composite scores	X	X	Bayley III: cognitive and language domains
	Adaptive functioning	X	X	ABAS III standard scores
	Number of adverse events	X	X	Verbal questionnaire, parent-report
SA 3: Metabo- Iomics	Primary Outcomes			

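### Exploratory Aim 3: the 5 pairs given for the before/after C14:1 test do not follow from the design, which gives 10 testosterone-first pairs, and the similar-power statement rests on an unstated assumption

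*Combined protocol and SAP*

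**What the plan says.** All references are to the combined protocol and SAP.

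- **Who is assayed, and when.** Section I, Specific Aim 3: "LCAC and BCAA will be quantified at baseline and 12 weeks in the first 20 subjects". Section IV.C (Overall study design) instead lists metabolomics among the assessments at baseline, 12 and 24 weeks. Table 2 marks both week 12 and week 24 for C14:1, the other long-chain acylcarnitines and the branched-chain amino acids.
- **Allocation.** Section IV.C (Randomization): infants are "randomized 1:1 using block randomization in groups of 20".
- **Two-group test.** Section IV.F will "compare C14:1 concentrations (an easily identified LCAC) between treatment groups at 12 weeks using two-sided t-tests", and states that "with 10 subjects per group we will have 80% power to detect a difference of 1.3 SD" at a two-sided alpha of 0.05.
- **Paired test.** The next sentence of section IV.F: "paired t-tests will be used to compare C14:1 before and after T treatment (5 paired samples), with similar power".
- **Untargeted panel.** Section IV.D describes more than 4,000 metabolites. Section IV.F claims over 80% power for two-fold differences between treated and untreated infants, and gives the threshold as follows: "using a significance level of 0.0001 (less than two false positives based on the conservative Bonferroni correction for multiple comparisons".
- **Named primary outcome.** Section IV.A and Table 2 give change in C14:1 from baseline, whereas the powered between-arm test in section IV.F compares 12-week concentrations.

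**The concern.** A sample size and a power claim sit next to each other, and neither can be derived from the rest of the plan. The sentence before uses 10 infants per group, and the paired test then uses 5 pairs without saying why half of the treated infants drop out of the count. The power is called similar without an SD of the paired difference or a within-infant correlation, and one of these is needed to compute power for a paired test.

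The stakes are modest. The before/after test is a follow-on analysis in an aim labelled exploratory. However, someone writing the analysis from this text has to guess which pairs count. A reader may also credit the test with about 80% power at 1.3 SD when that depends on an unstated quantity. The Bonferroni label carries a similar, smaller risk: many readers will take it to mean 5% familywise control over the panel.

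**Working it through.** **Step 1. The plan's own figure.** Inputs from section IV.F: n = 10 per group, d = 1.3 SD, two-sided alpha 0.05.

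- Noncentrality = d × √(n/2) = 1.3 × √5 = 2.907, with 18 df and critical t = 2.101.
- Power by noncentral t = 78.5%. The normal approximation gives Φ(2.907 − 1.960) = 82.8%.
- The stated 80% reproduces and is not disputed.

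**Step 2. How many pairs.** The first 20 infants form one block of 20 at 1:1, which gives 10 testosterone-first and 10 placebo-first infants. This matches the 10 per group in section IV.F. Baseline and week 12 span the testosterone period only in the testosterone-first arm, so there are 10 before/after pairs. Section IV.F, "Allowing for a 10% drop-out rate", sets that rate for Aim 1; if it is assumed here too, 10 × 0.9 = 9 pairs. If the week-24 targeted assays are done, placebo-first infants add up to 10 more pairs (weeks 12 to 24). None of these routes gives 5.

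**Step 3. Paired power when 1.3 is in SDs of the paired difference.** Noncentrality = 1.3 × √n, with n − 1 df, two-sided 0.05.

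| Pairs | Noncentrality | Power at 1.3 SD | SD detectable at 80% |
|---|---|---|---|
| 5 | 2.907 | 59.4% | 1.68 |
| 9 | 3.900 | 92.5% | 1.07 |
| 10 | 4.111 | 95.4% | 1.00 |

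The noncentrality for 5 pairs equals that for 10 per group, because √5 = √(10/2). The normal approximation therefore gives 82.8% for both. That may be where the 5 came from, but this is inference. The approximation is poor at 4 df, where critical t is 2.776 and not 1.960.

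**Step 4. Paired power when 1.3 is in between-infant SDs.** The effect in SDs of the difference is 1.3/√(2(1 − r)), where r is the within-infant correlation. The document gives no r, so these values are assumptions.

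| r | Effect in SDs of difference | Power, 5 pairs | Power, 10 pairs |
|---|---|---|---|
| 0 | 0.919 | 35% | 73% |
| 0.25 | 1.061 | 44% | 85% |
| 0.5 | 1.300 | 59% | 95% |
| 0.7 | 1.678 | 80% | 99.7% |
| 0.8 | 2.055 | 92% | >99% |

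Five pairs reach 80% at r = 0.70, and match the two-group 78.5% at r = 0.69.

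**Step 5. The 0.0001 threshold.** Taking m = 4,000 tests:

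- Expected false positives = 4,000 × 0.0001 = 0.4. The plan's limit of two would be reached only at 2/0.0001 = 20,000 tests.
- The 5% familywise Bonferroni level is 0.05/4,000 = 0.0000125. The level 0.0001 equals 0.05/500, eight times looser.
- If the tests were independent (an assumption), the chance of at least one false positive would be 1 − (1 − 0.0001)^4,000 = 33%.

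**The case against.** The strongest reply is that the similar-power statement may be true. The sentence before it speaks of SDs in a two-group comparison, so 1.3 can be read as a between-infant SD. At a within-infant correlation of about 0.7, 5 pairs then give 80%, and more at higher correlations. This stands. A reader might infer from the 59% that the plan's power claim is false. The document does not support that, because it does not define the SD for the paired test. What remains is that the claim depends on one unstated assumption and that the count of 5 has no source.

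On the threshold, the plan states its own criterion, an expected count of false positives, and 0.0001 meets it comfortably. It never claims 5% familywise control. A reader might infer that the untargeted screen is miscalculated or invalid, but the arithmetic is sound and only the label can mislead.

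It can also be said that the 5 is a parenthesis in a power statement, not an instruction to discard pairs, and that an analyst would use every available pair. That is fair, so no loss of data should be assumed. Comparing 12-week level rather than change is likewise a legitimate choice in a randomised comparison; the point there is only consistent naming.

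**Conclusion.** The point holds, at low severity. The design yields 10 testosterone-first pairs where the plan says 5, and nothing in the document accounts for the difference. This assumes that the first 20 infants fill the first block, which agrees with the plan's own 10 per group. With 5 pairs, power is 59% at 1.3 SD of the paired difference. It reaches about 80% only if 1.3 is a between-infant SD and the correlation is about 0.7.

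It would be wrong to conclude that the before/after test is underpowered as designed. With the 10 pairs that the design supplies, power at 1.3 SD of the difference is 95%, so the error understates the available information. Three smaller matters are editorial: the Bonferroni label, the week-24 targeted assays, and the level-or-change naming of the C14:1 outcome. Trial size, Aims 1 and 2 and the two-group 80% figure do not depend on any of this.

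**What to change.** 1. In section IV.F, delete the 5 pairs and the similar-power phrase. Suggested replacement: *Paired t-tests will compare C14:1 before and after testosterone in all infants with both samples. Ten testosterone-first pairs give 80% power at 1.0 SD of the paired difference (1.07 SD with 9 pairs, assuming the Aim 1 drop-out rate).*
2. Reconcile section I, Specific Aim 3 (baseline and 12 weeks) with section IV.C, Overall study design, and Table 2 (also 24 weeks). If week-24 targeted assays will be done, add that placebo-first infants contribute up to 10 further pairs from weeks 12 to 24, and say whether the two sets are pooled. If they will not be done, amend both section IV.C and Table 2.
3. Minor: keep 0.0001, but describe it as limiting expected false positives to about 0.4 per 4,000 tests, without the Bonferroni label. If familywise control is wanted, state the number of tests m and use 0.05/m.
4. Minor: name the same C14:1 outcome, 12-week level or change, in section IV.A, section IV.F and Table 2.

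Items 1, 3 and 4 are wording only. Item 2 is also wording only if it records what is already intended; a decision to run week-24 assays that were not planned would carry their laboratory cost.

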Studying tissue-specific gene expression and epigenetic modification in human infants is invasive and labor-intensive, however we can investigate circulating metabolites that reflect systemic pathway regulation. Pathways involved in energy metabolism are of specific interest in XXY. Long chain acylcarnitines (LCAC) are intermediate metabolites of fatty acid oxidation within the mitochondria. Obesity and insulin resistance are strongly associated with mitochondrial dysfunction and accumulation of LCAC. Branched chain amino acids (BCAA) also build up in the presence of mitochondrial dysfunction and are regarded as an excellent biomarker for obesity and insulin resistance. Work by one of my mentors, [name], has found that LCAC and BCAA are elevated in infants exposed to maternal obesity in utero, demonstrating abnormal metabolism from a very young age. We know maternal obesity is associated with insulin resistance in adult offspring and these metabolite differences in infancy represent the early metabolic programming that underlies childhood determinants of adult disease. This work and the work of others highlight the critical importance of *timing* of exposures on lifelong metabolic programming, and how metabolites can serve as early biomarkers of this process.

**Finally, T treatment for infants with XXY is becoming common despite a lack of scientific evidence to support this practice.** Samango-Sprouse et al reported that a cohort of boys with XXY who had received T in infancy had better neurodevelopment in early childhood. Largely because of this single study, many parents are requesting T for their XXY sons. These proactive parents are often successful in obtaining this treatment, reinforcing disparities in care without establishing if T is effective or safe in this population. A randomized and blinded trial of T is needed to fill these critical gaps and provide evidence for establishing standard of care.

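### The Aim 3 paired t-tests before and after T add age change to the T effect, so they cannot show what T induced; the randomised 12-week comparison that precedes them is sound

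*Combined protocol and SAP*

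**What the plan says.** Section I gives the purpose of Aim 3 as "To measure metabolite changes induced by T in infants with XXY", and the sampling as "LCAC and BCAA will be quantified at baseline and 12 weeks in the first 20 subjects".

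Section IV.F (Data Analysis Plan) sets out two C14:1 analyses.

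- **Lead analysis:** a comparison "between treatment groups at 12 weeks using two-sided t-tests". Its power statement is "with 10 subjects per group we will have 80% power to detect a difference of 1.3 SD with a two-sided alpha of 0.05".
- **Follow-on analysis:** "paired t-tests will be used to compare C14:1 before and after T treatment", described as "5 paired samples), with similar power".

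The remaining metabolites inherit both: "We will analyze secondary outcomes including other LCAC and BCAA (leucine, isoleucine, and valine) in a similar fashion".

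Section IV.A and Table 2 declare the primary outcome of Aim 3 as the change in C14:1 since baseline. Table 2 marks it at both week 12 and week 24. Section IV.D (Metabolomics) has the metabolites measured as concentrations. No age norm, age adjustment or placebo-arm change is attached to the paired test. By contrast, %BF in Aim 1 is converted to age-specific z-scores.

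**The concern.** A paired t-test in treated infants asks whether their mean change is zero. Under the visit schedule in Section IV.C, the baseline and 12-week samples fall at 4-12 weeks and about 5 months of age. Any change in C14:1 that comes with growth over that time is added to the effect of T, and without a placebo reference the two cannot be separated. If C14:1 falls with age, the test can favour T when T does nothing. If it rises, a real T reduction can be hidden.

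There is also a gap in the plan. The declared outcome is a change from baseline, but the lead test compares 12-week concentrations only. The paired test is the only C14:1 analysis described that uses the baseline value, and it leaves out the randomised control. Under Future Directions, the Aim 3 results are the basis for seeking funds to run metabolomics on all subjects, so a p-value misread as a T effect could carry forward.

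**Working it through.** **1. Reproduce the plan's figure.** Inputs from Section IV.F: 10 per group, 1.3 SD, two-sided alpha 0.05. For a two-sample t-test with 18 df, the noncentrality is 1.3 × √(10/2) = 2.91 and the critical value is 2.10. Power is 78.5%, and 80% is reached at 1.325 SD. The stated 80% is reproduced to within 2 points.

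**2. What each test estimates.** Write the mean change in treated infants as T effect + age change, and in placebo infants as age change alone.

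- Paired test: null is T effect + age change = 0.
- Between-arm comparison: the age change common to both arms cancels, leaving the T effect.

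This difference does not depend on sample size.

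**3. Size for the stated 5 pairs.** The documents give no C14:1 drift, so a range is assumed, in SDs of the within-infant change. The test has 4 df and critical value 2.776. The noncentrality is √5 × (T effect + drift), both in SDs of change. For example, with no T effect and drift 0.5 it is 2.236 × 0.5 = 1.12. With T effect -1.3 and drift +0.5 it is 2.236 × (-0.8) = -1.79.

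| Assumed upward drift (SD of change) | No T effect: chance of p < 0.05 | T effect -1.3 SD: chance of a significant decrease |
|---|---|---|
| 0 | 5.0% | 59.4% |
| 0.25 | 7.2% | 43.3% |
| 0.5 | 14.1% | 28.1% |
| 0.75 | 25.4% | 15.8% |
| 1.0 | 40.1% | 7.6% |

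The middle column is the same for downward drift. A simulation of 200,000 trials with no T effect agreed at drifts of 0.5 and 1.0 (14.1% and 40.5%).

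**4. The alternative, 10 v 10 on the same infants.**

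- *t-test on change scores.* In simulation, type I error stays at 5.0% for common drifts of 0, 0.5, 1.0 and 1.5 SD. Power at 1.3 SD of change is 78.5%, from the same noncentrality as in step 1.
- *Regression of the 12-week value on arm and baseline.* With SD of change set to 1 and before/after correlation r, the residual SD is √((1 + r)/2). At r = 0 it is 0.707, giving noncentrality 1.3/0.707 × √5 = 4.11 and power 97%. At r = 0.7 it is 0.922, giving 3.15 and power 84% (17 df). These values of r are assumed. Allowing for chance imbalance in baseline lowers both by roughly 1 to 2 points.

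**5. Units.** The plan's 1.3 SD is in SDs of the 12-week concentration, while steps 3 and 4 use SDs of change. The two coincide only at r = 0.5.

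**The case against.** The strongest reply is that the lead analysis already answers the question. It is randomised, the mechanistic reading in Section IV.F is attached to it, and the other LCAC and BCAA receive it as well. The paired test comes afterwards, in an aim labelled exploratory, and nothing in the documents says a T effect will be claimed from it alone. All of this stands, and it is why the point is minor. It does not make the paired test informative about T, and it does not supply a between-arm analysis of the declared change outcome.

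Three stronger readings are tempting, and the documents do not support them.

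- **That the documents show C14:1 drifting with age.** A reader might point to the untreated pilot infants, whose %BF z-score rose by 0.86 over 12 weeks (Section III), and to the statement that "Obesity and insulin resistance are strongly associated with mitochondrial dysfunction and accumulation of LCAC". The pilot figure is age-standardised and concerns another measure, so it shows departure from norms and not ordinary ageing. The quoted link is with obesity and insulin resistance. Neither gives a C14:1 trend.
- **That the error rates are those of 10 pairs.** Baseline and 12-week samples in 20 infants randomised 1:1 imply about 10 treated infants with both values, and 10 pairs at 1.0 SD drift would reject 80% of the time. The plan states 5 pairs, so the 5-pair figures apply. On the same basis, the alternative costs no power.
- **That the pairs certainly span about 2 to 5 months of age.** Section IV.F does not say which infants or visits form the 5 pairs. If they are placebo-first infants over weeks 12-24, the ages are about 5 to 8 months. The age problem is the same there, and Section IV.E already acknowledges that no control group exists in that period.

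**Conclusion.** The concern holds in a limited form. The paired tests of C14:1, other LCAC and BCAA confound T with age, so neither a significant nor a non-significant result from them bears on what T induced. That conclusion needs only the stated design. The size of the problem rests on assumed drift: 14% to 40% false-positive results with 5 pairs for drift of 0.5 to 1.0 SD of change, and power falling from 59% to 28% or 8% when that drift is upward and the true T reduction is 1.3 SD of change. With no drift the error rate is the nominal 5%.

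A reader might infer that Aim 3 as a whole cannot identify a T effect. It can, because its lead 12-week comparison between randomised arms is not biased by common age change. Severity is minor, given the exploratory label and that sound lead contrast.

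**What to change.** In the Aim 3 paragraph of Section IV.F:

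- Replace the paired t-tests for C14:1, other LCAC and BCAA with a regression of the 12-week value on treatment arm and baseline value in the same 20 infants (10 v 10). This supplies the missing between-arm analysis of the declared outcome and follows the baseline-adjusted regression that the plan already uses for %BF.
- State that conclusions about T effects come only from randomised between-arm contrasts.
- Show before/after changes descriptively for both arms, with no p-value attributed to T.
- Say which infants and visits the 5 pairs refer to. If they are placebo-first infants over weeks 12-24, report them descriptively only.

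The cost is a sentence or two, with no new infants, samples or assays. At 1.3 SD of change, the between-arm analysis has about 78% power on change scores, or about 84-97% with baseline adjustment under the assumed correlations. The stated 5 pairs have 59% even with zero drift, so no power is given up.

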### Specific Aim 1: To quantify the short-term effect of T in infants with XXY on cardiometabolic outcomes.

**Hypothesis:** Percent body fat (%BF) will follow a normal trajectory in treated infants, while infants not receiving T will have greater %BF. **Approach:** In the TESTO: Testosterone Effects on Short-Term Outcomes trial, infants with XXY (n=75) age 4-12 weeks will be randomized 1:1 to receive 25mg intramuscular T injections every 4 weeks for 3 doses or placebo. %BF will be assessed by air displacement plethysmography at baseline, 12 weeks, and 24 weeks. The primary outcome is change in %BF z-scores at 12 weeks between groups (powered to detect a difference of 0.5SD). Infants initially receiving placebo will get T in the second half of the study (12-24 weeks). Secondary outcomes include change %BF z-scores from 12-24 weeks, growth parameters, and serum leptin.

**Specific Aim 2: To quantify the short-term effects of T in infants with XXY on neurodevelopment, gonadal function and safety outcomes.**

**Hypothesis:** (1): XXY infants receiving T will have greater gains in standard scores on early motor skills, emerging language, and adaptive functioning. (2): T treatment will not impair gonadal function, as measured by gonadotropins and biomarkers of Sertoli cell function. (3): There will be no serious adverse outcomes associated with T treatment in infants with XXY. **Approach:** Infants from Aim 1 will be given standardized neurodevelopment assessments at baseline, 12 and 24 weeks. Serum hormone biomarkers of gonadal function will also be obtained at these times. Adverse events will be monitored throughout the study.

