## IV. Research Methods

### A. Outcome Measure(s):

#### Primary for Specific Aim 1

Change in %BF z-scores from baseline to 12 weeks (per PeaPod)

#### Primary for Specific Aim 2

Change in motor composite percentile on the AIMS assessment from baseline to 12 weeks

#### Primary for Specific Aim 3

Change in C14:1 long chain acylcarnitine (LCAC) from baseline

**Secondary outcomes:** Change in %BF z-scores from 12 to 24 weeks; change in anthropometric measurements from baseline to 12 and 24 weeks; change in gross and fine motor scaled scores from the PDMS; cognitive and language scores on the Bayley; adaptive functioning from the ABAS; serum hormones, lipids, BCAA, LCAC, and pathway analysis of untargeted metabolomics; urine metabolites; and number and type of adverse events.

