### C. Study Design and Research Methods

**Overall study design.** TESTO is a randomized controlled trial assessing the efficacy and safety of T injections in infants with a prenatal diagnosis of XXY. Body composition, neurodevelopment, serum hormones, safety parameters, and metabolomics will be assessed at baseline, 12 and 24 weeks into the

study. Infants will be randomized 1:1 to receive T vs placebo for the first 12 weeks of the study with the primary outcomes assessed after 12 weeks (Figure 5). The second half of the study will cross the treatment groups allowing us to evaluate if timing makes a difference in response and if initial benefits are sustained. This plan will optimize enrollment, as many parents will only participate if their son will get treatment, and allow us to maintain the blinded design.

**Setting.** The study will be conducted at Children’s Hospital Colorado (CHCO) in the outpatient Pediatric Clinical Translational Research Center (CTRC). CHCO is home to the eXtraordinary Kids Clinic, the first comprehensive interdisciplinary clinic for sex chromosome aneuploidies. The unique collaborative model and our expertise has led to national referrals and a high demand for clinical evaluations. We have successfully recruited hundreds of boys with XXY to participate in longitudinal and interventional research studies through close collaboration with family support groups and national/international experts in XXY. Our investigative team has expertise in child development, infant body composition, childhood disorders of insulin resistance, metabolomics, clinical trial recruitment, robust data acquisition and data analysis, making this the ideal setting.

[figure not shown]

Figure 5. Overall Study Design

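### The later %BF secondary outcome is a week-12-to-24 change in the text but a change from baseline in Table 2, and the timing question has no stated randomised contrast

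*Combined protocol and SAP*

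**What the plan says.** Three places in the combined protocol and SAP give one definition. Section I, Specific Aim 1: "Secondary outcomes include change %BF z-scores from 12-24 weeks, growth parameters, and serum leptin". Section IV.A, secondary outcomes: "Change in %BF z-scores from 12 to 24 weeks". Section IV.F, text for aim 1: "Secondary analyses will include change in %BF z-scores from 12 to 24 weeks".

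Section IV.F then splits that analysis by arm. One part is "in the group receiving T first (are the effects of T maintained or lost"; the other is "in the group receiving T second (does later T have the same effect". No between-arm test of the 12-to-24-week change is described.

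Table 2, in the same section, gives a different definition. Its first secondary row under SA 1 is "Change %BF z-scores from baseline", marked at week 24 only and separate from the week-12 primary row. Table 2 has no 12-to-24-week row, and the other three places have no baseline-to-week-24 %BF outcome.

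Section IV.C gives the purpose of crossing the arms: to "evaluate if timing makes a difference in response and if initial benefits are sustained". Section IV.E acknowledges that the second half has no control group, that its interpretation rests on assumptions, and that its outcomes are secondary.

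**The concern.** The two definitions use different reference points. The change from baseline starts from values that randomisation makes comparable, so its between-arm contrast at week 24 compares early with delayed T. The change from week 12 starts from a value that the first-period treatment may already have altered.

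This is not loose phrasing. Section IV.A keeps the reference points apart within one sentence: weeks 12 to 24 for %BF, and baseline to weeks 12 and 24 for anthropometrics. If both %BF quantities were intended, neither the text nor Table 2 is complete.

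At stake is the question that justifies the second half. With two declared definitions and no stated contrast for timing, the choice stays open until the data are seen, and a report of no difference at 24 weeks would be ambiguous unless its reference point were given.

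**Working it through.** **The plan's own figure.** Section IV.F sizes only the 12-week primary: 27 per group, 80% power, difference 0.5 z, spread 0.65. Treating 0.65 as an SD (the plan calls it a variance, but it equals the pilot SD):

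n = 2 × (1.960 + 0.842)² × 0.65² / 0.5² = 26.5, so 27 per group.

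Power at 27 is 80.7% (normal) or 79.2% (t), so the figure reproduces. No effect size, test or power is stated for the 24-week outcome under either definition.

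**Inputs.** Section III gives pilot 12-week changes in %BF z-score of +0.86 (SD 0.65) without T and -0.24 (SD 0.67) with T. It gives nothing on what follows after T is stopped, or on T started later.

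**Identity.** Let D be the T-first minus placebo-first difference in mean change; negative favours T-first. For the same infants,

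D(0–24) = D(0–12) + D(12–24).

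The two definitions therefore differ by D(0–12), whatever happens later. On pilot figures D(0–12) = -0.24 - 0.86 = -1.10 z, more than twice the 0.5 z used for sizing.

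**Scenarios.** The week 12–24 changes below are assumptions. Week-24 values add them to -0.24 (T-first) and +0.86 (placebo-first).

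| Assumed change, weeks 12–24 (T-first; placebo-first) | Week 24 from baseline | D(12–24) | D(0–24) |
|---|---|---|---|
| Pilot changes repeat by treatment (+0.86; -0.24) | +0.62; +0.62 | +1.10 | 0.00 |
| T-first unchanged, late T catches up fully (0; -1.10) | -0.24; -0.24 | +1.10 | 0.00 |
| Both arms rise, late T inert (+0.86; +0.86) | +0.62; +1.72 | 0.00 | -1.10 |
| T-first unchanged, late T inert (0; +0.86) | -0.24; +1.72 | -0.86 | -1.96 |
| T-first unchanged (0; -0.24) | -0.24; +0.62 | +0.24 | -0.86 |
| T-first rises by half the untreated change (+0.43; -0.24) | +0.19; +0.62 | +0.67 | -0.43 |
| T-first rebounds (+1.10; -0.24) | +0.86; +0.62 | +1.34 | +0.24 |

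Signs oppose only when D(12–24) lies strictly between 0 and +1.10, as in the fifth and sixth rows. The first two rows give the same pair of contrasts by different routes, so the within-arm changes still carry information that the week-24 contrast lacks.

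**Norms at week 24.** Section IV.D says the published z-score norms run from birth through 6 months. Section IV.B enrols at 31 to 90 days, and section IV.C sets visit 3 at 24 weeks (168 days) ± 10 days. The youngest possible age at that visit is 31 + 168 - 10 = 189 days; the oldest is 90 + 168 + 10 = 268 days. Six months is about 183 days. At scheduled visits every week-24 z-score lies beyond the cited norms, whichever definition is used.

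**The case against.** A reader might infer that the pilot figures show the two definitions giving opposite answers on timing, so that the choice between them decides the conclusion. The documents do not support that, for three reasons.

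- The pilot covers one 12-week period. Every week-24 value above rests on an assumption, and simple repetition of the pilot changes gives +1.10 against 0.00, not opposite signs.
- Section IV.F asks within-arm questions, and on those the definitions can agree. If placebo-first infants change by -0.24 on later T, later T matches early T; in the first row the baseline contrast of +0.62 v +0.62 also says that timing did not matter. If they change by +0.86, later T does not match; in the third row +0.62 v +1.72 also says that timing mattered. Conflict needs a between-arm test of the 12-to-24-week change that the plan does not specify.
- No test is declared for the 24-week outcome, so no power figure can be attached to either definition.

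It is also fair that the primary result will be reported, so with complete data a reader given either between-arm quantity can recover the other. The outcome is secondary, and section IV.E discloses the limits of the second half. Three places agree against one table, so correcting Table 2 alone would remove the contradiction.

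All of this limits the harm. It does not reconcile the definitions, and correcting Table 2 alone would delete the only listed outcome that gives the timing question a randomised comparison.

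**Conclusion.** The inconsistency is real and unreconciled: three statements of a 12-to-24-week change against one table row of change from baseline. As between-arm contrasts they differ by the first-period effect. That identity needs no assumption about weeks 12 to 24; its size of -1.10 z assumes that the pilot's 12-week difference holds in this trial. Whether the two would lead to different conclusions depends on assumptions that the pilot cannot inform: they may agree, differ, or in some cases take opposite signs. The second gap is that section IV.C's timing question has no stated randomised contrast, because section IV.F describes only uncontrolled within-arm changes. This concerns a secondary outcome and should be corrected; it does not touch the primary analysis.

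**What to change.** Before unblinding, align Specific Aim 1, section IV.A, the section IV.F text and Table 2 by listing two outcomes, each with its purpose:

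- Change in %BF z-score from baseline to week 24, compared between the randomised arms (early v delayed T), as the outcome for timing.
- Change in %BF z-score from week 12 to week 24 within each arm, as descriptive of maintenance (T-first) and of response to later T (placebo-first), with no randomised control claimed.

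Because week 24 falls beyond the cited norms, also report the week-24 contrast on absolute %BF, adjusted for baseline %BF and age. Section IV.F already plans a regression of this kind at 12 weeks, so this extends it to one more visit.

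Neither measure has to be dropped. The cost is wording in four places and one more labelled secondary analysis, with no new data or visits.
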